APPENDIX B: LOCAL SKIN REACTIONS

An assessment for local skin reactions is conducted by the investigator pre-treatment, immediately post-treatment and at all clinic visits following treatment. . The assessment is also used during the course of evaluating and reporting an AE that is a local skin reaction.

The overall scoring system is comprised of an erythema rating scale plus the addition of clinical descriptors adapted from Dykes, 1992 and the FDA Guidance for Industry: Skin Irritation and Sensitization Testing of Generic Transdermal Drug Products (1999). The severity of erythema is rated on a scale of 0–5 along with the presence of other clinical signs or symptoms. These descriptors noted by letters, are then added to the numerical score (e.g., 3S). *For example: Erythema spreading outside the treatment site with subject reporting scaling = 3 S*

Table 8: Skin Erythema Assessment

Rating	Description
0	No reaction/No erythema
1	Minimal erythema (barely perceptible)
2	Erythema (easily visible)
3	Erythema, spreading outside of treated site
4	Erythema, spreading outside of treated site with either edema (swelling) or vesicles (elevated, circumscribed lesions up to 1 cm in size that are filled with serous fluid)
5	Severe reaction with ulceration (irregularly sized and shaped erosions of the skin extending into the dermis)

Table 9: Clinical Signs/Symptom Descriptors*

Descriptor	Description
 O	No Clinical Signs/Symptoms
 BS	Burning or stinging (sensation as described by the subject)
 I	Itching (sensation as described by the subject)
 E	Edema
 S	Scaling
 F	Fissures
 C	Crusts
If C:	Give Color: _____
	Thickness:  thin  thick
	Describe:  dry  macerated  adherent  loose
	Culture Results:  positive  negative  N/A
 V	Vesicles
If V:	Give size _____ mm x _____ mm
 BU	Bulla
If BU:	Give size _____ mm x _____ mm
 P	Pustule
If P:	Give size _____ mm x _____ mm
 R	Erosion
If R:	Give size _____ mm x _____ mm
 U	Ulcer
 A	Scarring
If A:	 Contracture  Hypertrophic  Keloid
 OTH	Other
If OTH:	Describe Other:

*Clinical Symptoms are assessed as mild, moderate or severe per **Table 6** of this protocol.

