8.5.2 Blinding

Subjects in the randomized cohort will be blinded to the Study Arm to which they are randomized.

Site personnel will not be informed of the specific Study Arm assignment (they will only know the treatment # assigned); those administering the treatment will observe the treatment effect and the disposal process and may be unblinded as a result of their observations. This person will not conduct the follow-up assessments. These personnel will be instructed and trained not to reveal the assumed Study Arm assignment to any subject or to any of the other study personnel at the site. Site personnel completing follow-up evaluations will be different from the person who conducted the procedure and, therefore, will be blinded to the subject's treatment.

Subjects will be instructed (by subject handout Appendix G) not to discuss their assumed treatment assignment with anyone at the study site.

Only necessary persons at the sponsor shall know the treatment assignments and only those persons will have access to the database which holds the key for the treatment numbers distributed at each site. All others at the sponsor will remain blinded.

CANDESANT BIOMEDICAL	CLINICAL STUDY PROTOCOL SAHARA STUDY	Document #: CB-CLP-001 Revision: E
---------------------------------	---	---------------------------------------

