8.7.3 Immediately Post-Treatment

Immediately following patch removal, the treatment area will be thoroughly cleansed with water. A gauze pad soaked with water should be used to wipe the area a few times. This step should be repeated until the subject does not feel any residual effects, such as tingling or stinging. The subject should be asked to report their pain level using the Wong-Baker FACES pain scale during cleaning. The treatment area will be visually assessed by the physician, photographs may be taken, and any noted Adverse Events (AEs) will be documented.

Assessment for Local Skin Reactions: The investigator will evaluate axillary application sites for skin irritation to determine if there is an immediate reaction to the investigational device. If present it should be documented in accordance with the Skin Erythema Assessment and the Clinical Signs/Symptom Descriptors (**Appendix B**).

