When possible, subjects are to undergo follow-up visit evaluations at the same time of day of the week and around the same time of day as their baseline evaluations. In the event that the subject is not able to report on the same day as the baseline evaluations, the visit window permits the subject to report up to 1-3 days earlier or later than the target weekday. The visit windows are shown in **Table 3** below.

Table 3. Visit Windows

Visit	Window
24-hour phone call	± 12 hours
48-72 hour visit	± 1 day
2-week phone call	± 2 days
4-week, 6-week, 8-week, 10-week, 12-week visits	± 3 days

Follow-up evaluations to be conducted at follow-up visits are summarized below in **Table 4**.

Table 4. Follow-Up Assessments

Assessment	Time	Method	Reference
Daily Diary	Daily through 4-weeks	Written journal returned at 4-week visit	Appendix F
HDSS	Weekly	Visit or electronic	Appendix A
QoL Assessments	Weekly	Visit or electronic	Appendix C
Assessment for Local Skin Reactions	Immediately post treatment, AND, at every clinic visit	Visit required	Appendix B
GSP*	4-weeks ONLY	Visit required	Appendix D

**NOTE: If excess hair is present on the axilla at the 4-week visit, the hair shall be clipped prior to conducting GSP testing. Stubble or minimal hair is acceptable. GSP should be measured in accordance with the instructions and training provided by the sponsor. Any deviation from this procedure should be documented and explained.*

Table 5 summarizes the subject schedule for the study.

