9.2 Study Design, Randomization and Blinding

The Sahara Study is a prospective, multi-center, randomized, blinded, pivotal study to evaluate the safety and effectiveness of the N-SWEAT Patch.

Subjects with primary axillary hyperhidrosis or excessive sweating (defined by a score of 3 or 4 on the HDSS), who have provided informed consent and have met the study eligibility criteria, will participate. Up to 120 adult subjects will be enrolled. The first 10 subjects will be treated with the N-SWEAT patch and constitute the roll-in cohort and up to 110 subjects will be randomized to 1 of 2 treatment groups in a 1:1 ratio to receive a single administration of the N-SWEAT Patch or a sham control patch. The randomization will be blocked by investigational center and stratified by HDSS 3 vs. 4 at baseline. Up to 10 additional subjects may be enrolled to account for loss to follow up or other missing and critical data.

Randomized subjects will be blinded to their treatment assignment. Site personnel administering the treatment will observe the treatment effect and the disposal process and may be unblinded as a result of their observations. This person will not conduct the follow-up assessments and will not reveal the assumed treatment assignment to the subject, other site personnel, or the investigator at any time during the study follow-up period. Study subjects and study staff will be instructed not to discuss assumptions about the treatment received.

The sponsor will identify those who need to be unblinded in order to conduct the study. All others at the sponsor will remain blinded.

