10.2 Adverse Event Review by Investigator

Each AE will be assessed by the investigator as to its relationship and level of relatedness to the device and/or procedure. In addition, the investigator will identify the date of onset, any required treatment or intervention, severity, and duration. All AEs will be monitored until they are adequately resolved, stabilized and/or explained.

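### The same role, the investigator, scores the skin right after patch removal and at every later clinic visit, and nothing requires two different people, so blinded follow-up skin scoring is not secured

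*Protocol*

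**What the plan says.** **Skin scoring.** Appendix B gives the whole series of local skin reaction scores to one role: "An assessment for local skin reactions is conducted by the investigator pre-treatment, immediately post-treatment and at all clinic visits following treatment". Protocol section 8.7.3, which is part of the Procedure section, says of the moment after removal: "The investigator will evaluate axillary application sites for skin irritation to determine if there is an immediate reaction to the investigational device". Table 4 in section 8.8 sets the same timing without naming an assessor: "Immediately post treatment, AND, at every clinic visit".

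**Blinding.** Protocol section 8.5.2 says that "those administering the treatment will observe the treatment effect and the disposal process and may be unblinded as a result of their observations". It then relies on a separation of people: "Site personnel completing follow-up evaluations will be different from the person who conducted the procedure and, therefore, will be blinded" to the assignment. Section 9.2, repeated in SAP section 2, adds that the person who treats "will not reveal the assumed treatment assignment to the subject, other site personnel, or the investigator" while follow-up continues. SAP section 7 has investigators stay blinded to the end of the study, even after the sponsor is unblinded for the 4-week analysis.

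**Adverse events (AEs).** Section 10.2 opens: "Each AE will be assessed by the investigator as to its relationship" to the device or procedure. The investigator also rates severity on Table 6. For the safety summary, SAP section 10 uses events as classified by the DSMB, with DSMB severity and DSMB-adjudicated relatedness. Time to resolution stays as the investigator reports it.

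**The concern.** The blinding rule protects follow-up assessment by excluding the person who carried out the procedure. The skin-scoring instructions bring a second role, the investigator, to the axilla just after the patch comes off, to look for an immediate reaction. That is close to the observation that section 8.5.2 says can unblind. The same role is then named for the scores at 48-72 hours, at week 4 and at later clinic visits.

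Local skin reactions and adverse events are the primary safety outcome. Protocol section 9.9 and SAP section 10 review them for overall acceptability, without a hypothesis test. The reading of active against sham therefore depends on assessor judgement, and expectation about the arm can move that judgement in either direction.

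**Working it through.** No arithmetic tests this point. The check sets the role assignments beside the blinding rules.

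**Step 1: who looks, and when.**

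| Moment | Role named | Source |
|---|---|---|
| Before treatment | Investigator | Protocol 8.2, 8.3.1, Appendix B |
| Application | Trained medical professional | Protocol 8.7 |
| Visual check after removal | Physician | Protocol 8.7.3 |
| Immediate skin score | Investigator | Protocol 8.7.3, Appendix B |
| Skin score at clinic visits | Investigator | Appendix B |
| AE severity and relatedness at site | Investigator | Protocol 10.2 |

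**Step 2: who must be blinded.** Follow-up evaluators (synopsis and 8.5.2) and investigators (9.2, SAP sections 2 and 7). The only operative exclusion is that follow-up evaluators are "Site personnel completing follow-up evaluations will be different from the person who conducted the procedure".

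**Step 3: try each way of staffing a site.**

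- *The investigator applies the patch.* Appendix B then has the operator scoring at follow-up, which 8.5.2 does not allow.
- *Someone else applies it, and one investigator scores throughout.* The wording of 8.5.2 is met. The follow-up scorer has nevertheless inspected the skin just after removal. Section 8.7.4 repeats all steps for the second axilla at the same visit. In the written order, the first axilla is therefore scored before the second is treated.
- *Different investigators do the immediate and follow-up scores.* Both the wording and the intent are met. Section 13.5 allows additional investigators, but no passage requires this split.

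Only the third arrangement secures the intended blind, and it is optional.

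**Step 4: how many scores are exposed.** After treatment there are 2 required clinic visits (48-72 hours and week 4) and 4 recommended ones that may be held by phone (weeks 6, 8, 10 and 12). That gives 2 to 2 + 4 = 6 scheduled follow-up skin scores per subject. The randomised maximum of 110 subjects is a ceiling on who could be affected, not an estimate.

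**Step 5: which outcomes are reached.**

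- *Visit-level skin scores:* directly. No passage has the DSMB examine subjects.
- *Investigator-reported AE inputs:* partly. Reports and photographs come from the sites (10.3). The stopping rule after 10 subjects counts severe device-related events by Table 6, the scale that investigators use.
- *Primary endpoint:* not shown. The Hyperhidrosis Disease Severity Scale is answered by the subject, and Table 5 lists site administration only in the first two visit columns.
- *Gravimetric sweat production:* not shown. No passage names who measures it. The result is a weighed filter paper, and the fourth secondary endpoint tests the active arm against zero rather than against sham.

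**The case against.** The strongest reply is that no rule is breached. Section 8.5.2 bars only the person who carried out the procedure, and section 9.2 bars that person from disclosing an assumption. Looking at skin does neither. The documents do not say that the investigator applies the patch, and a site may have several investigators. This reply stands against the inference, which a reader might draw, that the protocol contradicts its own blinding rule. A site can comply with every sentence. What is missing is a requirement that would secure the stated aim.

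The mechanism is also unproven. No passage says that skin appearance reveals the arm. In the two earlier studies, 12 and 8 subjects received the active patch, and 3 device-related events were reported, all skin reactions. Transient redness may not have been counted, so these figures neither establish unblinding nor exclude it. Section 8.7.3 does not place the investigator at the cleaning, and only the synopsis lists disposal among the steps repeated for each axilla. A reader should therefore not conclude that follow-up assessors are in fact unblinded, or that all 110 subjects are affected.

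DSMB adjudication is a real safeguard. Section 10.4 describes its monthly review as blinded, section 10.3 requires standardised photographs of skin reactions reported as AEs, and SAP section 10 analyses the board's severity and relatedness. It is partial, because the board depends on what sites record and does not repeat the visit scores.

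A reader might also infer bias in the primary endpoint through cueing of subjects. Scores are self-reported, and both staff and subjects are told not to discuss the assumed assignment. The documents give no support for that step.

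**Conclusion.** The point holds as a gap in role separation. Section 8.7.3 and Appendix B put one role in both positions and do not require different individuals, while sections 8.5.2 and 9.2 and SAP section 7 intend that role to stay blinded. The consequence is a risk of functional unblinding, mainly in visit-level local skin reaction scores and, less directly, in investigator-reported AE inputs.

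No numerical bias can be given, and its direction is not predictable. The conclusion rests on two assumptions: that skin seen just after removal carries some information about the arm, and that at least some sites use the same individual for both tasks. It does not extend to the primary endpoint or to gravimetric sweat production. It is worth correcting because skin reactions belong to the primary safety outcome and the correction costs little. Label: cheap improvement.

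**What to change.** In protocol sections 8.5.2 and 8.7.3 and Appendix B, state that:

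1. Whoever performs the immediate post-treatment Appendix B score counts as procedure personnel for that subject.
2. A different trained person, who was not present at any time from patch application through cleaning and disposal, performs the Appendix B scoring at the 48-72 hour, week 4 and later clinic visits.

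Leave the physician's immediate safety check as it is. Leave access to treatment-day information for AE care and relatedness unchanged too, because Table 7 relies on timing and on whether the event abates after removal. Barring everyone present on treatment day from AE rating is not proposed either. Given the physician check in 8.7.3, it could force a second physician at some sites. Some exposure of site AE ratings therefore remains, with DSMB adjudication as the safeguard.

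**Cost.** The change is to wording and to the delegation log. Section 8.5.2 already implies at least two people per site. A second staff member must be trained on the Appendix B scale, and sites with one investigator have less freedom in assigning tasks. Appendix B must also allow a trained scorer other than the investigator at follow-up.

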APPENDIX C: QoL SURVEYS

Information and Instructions for Study Subjects:

About Sweating:
Sweating is a natural and healthy part of life. Sweating helps to cool the body and maintain a normal body temperature in a warm environment or during exercise. It is normal to sweat when you are hot, when you are exercising, and when you are feeling stressed.
About Excessive Sweating:
You are in this study because you feel like you sweat too much. You may sweat at times other than when you are warm, exercising, or stressed. The questions below are designed to measure the severity and impact of your excessive underarm sweating during the past week. While you may experience excessive sweating on other parts of your body, these questions are designed to measure the impact of the treatment on your underarm sweating ONLY.
Instructions:

 Please only think about your underarm sweat as you answer these questions. Please remember that sweating when you are hot, exercising or stressed is normal, so when you are answering the questions, think about sweating that is beyond normal. For example, you may sweat when you work out at the gym and still answer "never" since sweating at the gym during a strenuous workout is considered to be the body's natural response to keep the body cool. If you have any questions, you may contact the study team

QUALITY OF LIFE ASSESSMENT QUESTIONS		Version: Draft IDE Submission	
TIME OF ASSESSMENT:  Baseline  1 week  2 weeks  3 weeks  4 weeks  5 weeks  6 weeks  7 weeks  8 weeks  9 weeks  10 weeks  11 weeks  12 weeks  Other	BOTHER: During the past week how bothered were you by your underarm sweating?	 Not at all bothered  A little bothered  Moderately bothered  Very Bothered  Extremely Bothered	
	IMPACT: During the past week how often did your underarm sweating impact your daily activities?	 Not at all  A little bit  A moderately amount  A great deal  An extreme amount	
	QoL-7: How has your underarm sweating impacted certain areas of your life over the past week? Please indicate Yes or No to the following statements		
	1. I felt embarrassed because of my underarm sweating		 Y  N
	2. I felt frustrated because of my underarm sweating		 Y  N
	3. I felt less confident because of my underarm sweating		 Y  N
	4. I had to change my shirt during the day because of my underarm sweating		 Y  N
	5. I had to take more than 1 shower or bath a day because of my underarm sweating		 Y  N
	6. My underarm sweating kept me from doing an activity that I wanted or needed to do		 Y  N
7. I wanted to avoid interactions with other people because of my underarm sweating		 Y  N	

CANDESANT BIOMEDICAL	CLINICAL STUDY PROTOCOL SAHARA STUDY	Document #: CB-CLP-001 Revision: E
-------------------------	---	---------------------------------------

APPENDIX D: GSP INSTRUCTIONS

Materials Required

- Quantitative Filter Papers, 90 mm
- Room temperature environment (26°C-30°C recommended). Actual room temperature must be documented to ensure that the same temperature is applied for each gravimetric test.

Procedure

GSP should be measured at screening, baseline (~72 hours later) and at the 4-week follow-up visit. Measurements should be performed in the same position(s) (sitting, standing, or walking) at every visit. The position used should be document in the subject records. If the screening GSP Measurement and the Baseline GSP Measurement differ by more than 100%, the subject should not be enrolled. GSP should not exceed 300 mg/5 min in either axilla at either screening or baseline

IMPORTANT: Each gravimetric measurement must be taken in similar room conditions (same humidity and temperature as baseline). Whenever possible all Gravimetric tests for this study (screening, baseline and 4-weeks) should be taken at the same time of day (± 3 hours).

A minimum of two (2) measurements should be taken in each axilla at every timepoint to ensure accuracy of results. If following the 2nd readings there is concern regarding the measurement accuracy, a 3rd reading may be performed. An average of accurate reading(s) will be reported.

- Weigh the plastic tube (vial) with filter paper to be used for the assessment (in milligrams) and document the baseline combined weight of the filter paper and vial.
- Dry the subject's axilla with an absorbent tissue or similar. Allow subject to sit for 15 minutes at room temperature (20-25.6°C)
- Determine the planned treatment area and desired location for filter paper placement. Paper should be placed centrally, just under the axilla crease formed when arms are down by their side.
- Place the previously weighed filter paper in the subject's armpit and ask them to hold it there for 5 minutes.

Following the 5-minute application of the filter paper, the filter paper and vial together will be weighed again. The result is the difference in the weight from baseline filter paper and vial weight and post filter paper application (paper placed in vial and weighed). The difference is calculated in milligrams and recorded as mg/5mins.

APPENDIX E: FITZPATRICK SKIN TYPE

The subject will be evaluated by the study site to determine their Fitzpatrick skin type based upon the categories as described below. The resulting skin type will be entered into the subjects CRF.

Skin Type I

Pale white skin, blue/green eyes, blond/red hair
Always burns, does not tan

Skin Type II

Fair skin, blue eyes
Burns easily, tans poorly

Skin Type III

Darker white skin
Tans after initial burn

Skin Type IV

Light brown skin
Burns minimally, tans easily

Skin Type V

Brown skin
Rarely burns, tans darkly easily

Skin Type VI

Dark brown or black skin
Never burns, always tans darkly

APPENDIX F: SAMPLE PATIENT DIARY

Daily Diary

[figure not shown]
[figure not shown]
[figure not shown]
Please remember to bring this diary to your 4-week follow-up appointment.

SAHARA STUDY

DAILY LOG: Week 1		SUBJECT ID: _____					
Day #	Date	PLEASE INDICATE ANY SYMPTOMS THAT YOU FEEL IN YOUR UNDERARMS					
1		 None, I feel fine  I have a continuing Symptom... OR  I have a NEW Symptom – Indicate Symptoms on the list below by Day #					
2		 None, I feel fine  I have a continuing Symptom... OR  I have a NEW Symptom – Indicate Symptoms on the list below by Day #					
3		 None, I feel fine  I have a continuing Symptom... OR  I have a NEW Symptom – Indicate Symptoms on the list below by Day #					
4		 None, I feel fine  I have a continuing Symptom... OR  I have a NEW Symptom – Indicate Symptoms on the list below by Day #					
5		 None, I feel fine  I have a continuing Symptom... OR  I have a NEW Symptom – Indicate Symptoms on the list below by Day #					
6		 None, I feel fine  I have a continuing Symptom... OR  I have a NEW Symptom – Indicate Symptoms on the list below by Day #					
7		 None, I feel fine  I have a continuing Symptom... OR  I have a NEW Symptom – Indicate Symptoms on the list below by Day #					
DETAILS:	Day 1	Day 2	Day 3	Day 4	Day 5	Day 6	Day 7
Notes:	 Pain  Itch  Redness  Peeling skin  Blister  Infection (pus, discharge)  Fever  Other _____	 Pain  Itch  Redness  Peeling skin  Blister  Infection (pus, discharge)  Fever  Other _____	 Pain  Itch  Redness  Peeling skin  Blister  Infection (pus, discharge)  Fever  Other _____	 Pain  Itch  Redness  Peeling skin  Blister  Infection (pus, discharge)  Fever  Other _____	 Pain  Itch  Redness  Peeling skin  Blister  Infection (pus, discharge)  Fever  Other _____	 Pain  Itch  Redness  Peeling skin  Blister  Infection (pus, discharge)  Fever  Other _____	 Pain  Itch  Redness  Peeling skin  Blister  Infection (pus, discharge)  Fever  Other _____
IF YOU EXPERIENCE ANY OF THESE SYMPTOMS, PLEASE CALL YOUR PHYSICIAN RIGHT AWAY!!							

Appendix G: Sample Subject Take Home Care Hand-Outs**4. Post-Screening Postcard (CB-CLO-001.4, RevA)**

2. Post-Treatment Hand-out (CB-CLO-001.2, Rev B)

[figure not shown]

